2.4.5.5 Analyses of electrocardiogram variables

Not Applicable.

2.4.5.6 Analysis of Tanner stages measurement

Boys-development of external genitalia, girls-breast development, boys/girls -pubic hair stages as well as a global Tanner puberty classification (Prepubescent, Pubescent and Postpubescent) will be described by analysis visit using count and percentage.

The change from baseline in Tanner stage based on development of external genitalia for boys, and breast development for girls by analysis visits will be assessed (No change in Tanner stage, change in Tanner stage ≥ 1).

In addition, number of post-menarchal girls at baseline and during the study will be summarized.

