7.2.1 Exclusion criteria related to study methodology

E 01. Children and adolescents aged less than 8 years or more than 17 years at the time of informed consent signature unless different local regulation applies (eg, for Russia only: patients aged less than 12 years or more than 17 years at the time of informed consent signature).

Note: Patients aged of 8 to less than 10 years who have not had previous attempts to lower LDL-C by other means will be excluded.

E 02. Patients with LDL-C less than 130 mg/dL (3.37 mmol/L) (ie, adequately controlled) obtained during the screening period after the patient has been on stable LMT (ie, stable optimal dose of statin ± other stable LMTs, or stable non-statin LMTs in statin intolerant patients) treatment for at least 4 weeks.

Note: Patients who have previously participated in the DFI14223 study have already met this LDL-C requirement when they screened for the DFI14223 study and thus will not be excluded based on LDL-C <130 mg/dL (3.37 mmol/L).

- E 03. Patients with body weight less than 25 kg.
- E 04. Patients aged of 8 to 9 years not at Tanner Stage 1 and patients aged of 10 to 17 years not at least at Tanner Stage 2 in their development (See Appendix B).
- E 05. Daily dose of statin that is above the maximum recommended dose for pediatric patients as per the local prescribing label.
- E 06. Patients who will receive statin de novo during the run-in period.
- E 07. Use of nutraceutical products or over the counter therapies that may affect lipids which have not been at a stable dose for at least 4 weeks prior to the screening visit.
- E 08. Patients not previously instructed on a cholesterol-lowering diet prior to the screening visit.
- E 09. Patients with secondary hyperlipidemia (such as decompensated hypothyroidism, nephrotic syndrome, obstructive liver disease, anorexia nervosa, obesity, and drug treatment [eg, isotretinoids]).
- E 10. Patients diagnosed with homozygous familial hypercholesterolemia.
- E 11. Patients who have received lipid apheresis treatment within 2 months prior to the screening period, or have plans to receive it during the study.
- E 12. Patients with uncontrolled (ie, HbA1c levels above local guidelines or equivalent) Type 1 or 2 diabetes mellitus.

- E 13. Patients with known uncontrolled thyroid disease (ie, thyroid stimulating hormone levels above or below the laboratory's reference range within the past 6 months that were obtained due to clinical indication).

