Appendix B Tanner stages

The Tanner stages assessment for each patient at each site should be performed, if possible by the same investigator/designee trained to assess pubertal development (1, 2).

- Boys development of external genitalia
 - Stage 1: Pre-adolescent. Testes, scrotum, and penis are of about the same size and proportion as in early childhood.
 - Stage 2: The scrotum and testes have enlarged and there is a change in the texture of the scrotal skin. There is also some reddening of the scrotal skin.
 - Stage 3: Growth of the penis has occurred, at first mainly in length but with some increase in breadth. There has been further growth of testes and scrotum.
 - Stage 4: Penis further enlarged in length and breadth with development of glans. Testes and scrotum further enlarged. There is also further darkening of the scrotal skin.
 - Stage 5: Genitalia adult in size and shape. No further enlargement takes place after Stage 5 is reached.

• Girls - breast development

- Stage 1: Pre-adolescent; elevation of papilla only.
- Stage 2: Breast bud stage; elevation of breast and papilla as a small mound, enlargement of areola diameter.
- Stage 3: Further enlargement of breast and areola, with no separation of their contours.
- Stage 4: Projection of areola and papilla to form a secondary mound above the level of the breast.
- Stage 5: Mature stage; projection of papilla only, due to recession of the areola to the general contour of the breast.

• Boys/Girls - pubic hair

- Stage 1: Pre-adolescent; the vellus over the pubes is not further developed than that over the anterior abdominal wall, ie, no pubic hair.
- Stage 2: Sparse growth of long, slightly pigmented, downy hair, straight or only slightly curled, appearing chiefly at the base of the penis (boys) or along the labia (girls).
- Stage 3: Considerably darker, coarser, and more curled. The hair spreads sparsely over the junction of the pubes.
- Stage 4: Hair is now adult in type, but the area covered by it is still considerably smaller than in most adults. There is no spread to the medial surface of the thighs.
- Stage 5: Adult in quantity and type, distributed as an inverse triangle of the classically feminine pattern (girls). Spread to the medial surface of the thighs, but not up the linea alba or elsewhere above the base of the inverse triangle.

BIBLIOGRAPHIC REFERENCES

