2.1.4.6 Tanner stage measurement

Tanner stages measurement include assessments of boys–development of external genitalia, girls breast development, boys/girls –pubic hair, performed if possible, by the same investigator/designee trained to assess pubertal development, during:

- Run-in (if needed) at Visit 1 (up to Week -6) or Screening at Visit 2 (up to Week -2).
- The double-blind period at Visit 7 (Week 24)/or early termination.
- The OL period at Visit 9 (Week 44), Visit 11 (Week 68) and Visit 14 (Week 104)/or early termination for patients proceeding into OL period.

In addition, a global Tanner puberty classification as Prepubescent [Tanner stage = 1], Pubescent

[Tanner stage ≥ 2 to 4] and Postpubescent [Tanner stage = 5]) will be derived, based on breast development stage for girls and external genitalia stage for boys as it is commonly reported in the literature that in most children the first signs of puberty is breast development for girls and external genitalia for boys (4, 5, 6).

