2.4.5 Analyses of safety data

No formal inferential testing will be performed for either study period. Summaries will be descriptive in nature. All summaries of safety results described below will be presented for each study period respectively, unless otherwise noted.

General common rules

All safety analyses will be performed on the safety population for the double-blind period and on the OL population for the OL period, as defined in Section 2.3.2 unless otherwise specified, using the following common rules:

- Safety data in patients who do not belong to the safety population (ie, exposed but not randomized) will be listed separately.
- The baseline value for both double-blind and OL periods is defined as the last available value obtained up to the date and time of the first double-blind IMP injection in EFC14643 study, except otherwise specified.
- PCSA values are defined as abnormal values considered medically important by the Sponsor according to predefined criteria/thresholds based on literature review and defined by the Sponsor for clinical laboratory tests and vital signs, PCSA in children [Appendix A] and PCSA in adults version dated May 2014 [Appendix B]). Considering that the threshold defined in the PCSA list for monocytes and basophils can be below the ULN, the following PCSA criteria will be used for the PCSA analysis of monocytes and basophils:
 - PCSA criterion for monocytes: >0.7 Giga/L or > ULN (if ULN ≥ 0.7 Giga/L)
 - PCSA criterion for basophils: >0.1 Giga/L or > ULN (if ULN \ge 0.1 Giga/L)
- PCSA criteria will determine which patients had at least 1 PCSA during the TEAE period, taking into account all evaluations performed during the TEAE period, including nonscheduled or repeated evaluations.
- The treatment-emergent PCSA denominator by group for a given parameter will be based on the number of patients assessed for that given parameter at least once during the TEAE period.
- All measurements, scheduled or unscheduled, fasting or not fasting, will be assigned to analysis windows defined in Section 2.5.4, Table 5 and Table 6 in order to provide an assessment for Week 4 to Week 104 time points.

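### The Tanner change-from-baseline table counts patients already at stage 5 as unchanged and has no category for a lower stage

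*SAP*

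**What the plan says.** SAP 2.4.5.6 plans two Tanner summaries.

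- The genital, breast and pubic-hair stages, with a global puberty class, "will be described by analysis visit using count and percentage".
- The change from baseline, using genital stage for boys and breast stage for girls, "by analysis visits will be assessed (No change in Tanner stage, change in Tanner stage" of at least 1).

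The general safety rule in SAP 2.4.5 sets the population: "All safety analyses will be performed on the safety population for the double-blind period and on the OL population for the OL period". SAP 2.4.5.6 does not narrow it by baseline stage.

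The last puberty class in SAP 2.1.4.6 is "Postpubescent [Tanner stage = 5]) will be derived", so the SAP expects stage 5 patients. Protocol Appendix B treats stage 5 as the end of the scale; for boys it adds "No further enlargement takes place after Stage 5 is reached". Protocol 7.2.1 excludes 8- to 9-year-olds who are not at stage 1, and "patients aged of 10 to 17 years not at least at Tanner Stage 2 in their development". That is a minimum from age 10, with no maximum, in a trial that enrols up to age 17.

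**The concern.** The question for this table is whether puberty advances as expected on treatment. A patient at stage 5 cannot answer it. Placed in the no-change category, that patient is indistinguishable from a child at stage 2 or 3 who has not advanced, and the second child is the one of interest.

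A stage re-rated below baseline is foreseeable, because Protocol 9.2.4.6 and SAP 2.1.4.6 ask for the same assessor only where possible. The two categories give the programmer no rule for it.

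Tanner stage is a named safety endpoint (Protocol 9.2.4), and this is the only planned table of within-patient change in stage. The SAP limits or splits comparable tables elsewhere. In SAP 2.4.5.3 the hormone summaries are confined to boys at stage 2 or above and to girls at least a year past menarche, and the incidence of abnormal laboratory values may be shown by baseline status.

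**Working it through.** The plan gives no figure for the Tanner table, so there is none to reproduce.

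**Inputs from the documents.** Planned arms are 50 alirocumab and 25 placebo per cohort (Protocol 11.1), hence 100 and 50 pooled. Week 24 is the only placebo-controlled Tanner visit after baseline (Protocol 1.3).

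**Assumed inputs.** The share at stage 5 at baseline, q, runs from 10 to 50%. For dilution, progression among patients below stage 5 is 30% on placebo and 15% on alirocumab. For distortion, it is 30% in both arms. Change is read as signed, so a stage 5 patient never counts as change of at least 1.

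**Step 1, dilution.** Percentage shown = (1 − q) × percentage among patients below stage 5. At q = 30%: 0.70 × 30% = 21.0% and 0.70 × 15% = 10.5%. The difference is 10.5 points instead of 15, and the ratio is 0.50 either way.

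**Step 2, distortion.** With equal true progression r in both arms, the spurious difference is r × (difference in q between arms). Randomization makes that difference zero on average. Its 95% limits are ±1.96 × √[q(1 − q)(1/n1 + 1/n2)]. At q = 30%:

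- Per cohort: 1.96 × √(0.21 × 0.06) = 0.220, and × 0.30 = 6.6 points.
- Pooled: 1.96 × √(0.21 × 0.03) = 0.156, and × 0.30 = 4.7 points.

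| q | Shown, placebo / alirocumab | Difference (true 15) | Ratio | Spurious difference per cohort | Spurious difference pooled |
|---|---|---|---|---|---|
| 10% | 27.0% / 13.5% | 13.5 | 0.50 | ±4.3 | ±3.1 |
| 20% | 24.0% / 12.0% | 12.0 | 0.50 | ±5.8 | ±4.1 |
| 30% | 21.0% / 10.5% | 10.5 | 0.50 | ±6.6 | ±4.7 |
| 40% | 18.0% / 9.0% | 9.0 | 0.50 | ±7.1 | ±5.0 |
| 50% | 15.0% / 7.5% | 7.5 | 0.50 | ±7.2 | ±5.1 |

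**Step 3, how often a large imbalance arises.** For a gap of at least 20 points in the stage 5 share, z = 0.20 / √[q(1 − q)(1/n1 + 1/n2)], with q from 20 to 40%:

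- Per cohort: z = 2.04 to 1.67, two-sided probability about 4 to 10%.
- Pooled: z = 2.89 to 2.36, probability about 0.4 to 1.8%.

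**Step 4, loss of information.** No test is planned, so this is illustration only. For 30% versus 15%, pooled and two-sided 0.05, power is 42.2% over all patients and 44.5% over those below stage 5, at q = 30%. Across the range of q the gap is about 1 to 3 points.

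**The case against.** The strongest reply is that the information is largely there already. The puberty class uses the same scales as the change table and is tabulated by visit, and SAP 2.1.1 says baseline safety parameters are shown with the safety summaries. A reader could therefore compute n(change ≥1) / (N − n at stage 5 at baseline). SAP 2.4.5.3 also lists hormone values with Tanner stage for every girl and boy, so a mature adolescent and a stalled child can be told apart case by case. Safety is descriptive with no formal test, results are also pooled across cohorts, and height and BMI percentiles do not share this ceiling.

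Most of this stands. Recovery is exact only if few values are missing, and marginal counts by visit show neither decreases nor progression by starting stage. Randomization is stratified by body weight, which plausibly tracks maturity, so the imbalance figures above are probably on the high side.

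A reader might infer that the growth-safety comparison as a whole is diluted or distorted, or that the table favours one arm. The documents do not support either. One table is affected, the ceiling acts on both arms alike on average, and any chance imbalance should be visible in the baseline puberty classes. Nor do the documents fix a size: they give neither the stage 5 share nor an expected progression rate.

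**Conclusion.** The gap in the table definition follows directly from the text and needs no assumption beyond reading change as signed. Its numerical effect is conditional. Percentages and their difference shrink by 10 to 50% if the stage 5 share is 10 to 50%, while the expected ratio does not move. Spurious differences stay within about 4 to 7 points per cohort, or 3 to 5 points pooled, at the 95% limits, if true progression is 30% in both arms. No test or efficacy conclusion depends on this table. Severity is minor. The change is still worth making, because it gives a more accurate progression rate for a paediatric safety endpoint from data already collected.

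**What to change.** In SAP 2.4.5.6:

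- Report the proportion with change of at least 1 among patients at baseline stage 1 to 4 on the scale used (genitalia for boys, breast for girls).
- Preferably show this as a shift table by baseline stage.
- Show patients at stage 5 at baseline separately, as not able to advance.
- Give decreases from baseline their own row.

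The cost is a few lines of SAP text and a smaller denominator in this table. No new data are needed.

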2.4.5.7 Analyses of Cogstate Battery test

Cognitive scores (including by domains: DET [Psychomotor Function], IDN [Attention]; [OCL; Visual Learning]; GML [Executive Function]) and composite score will be described on the safety population by treatment for the double-blind period.

The change from baseline will be described for each score and the composite score.

The absolute change from baseline in the composite score at Week 24 will be analyzed using an ANCOVA model, with unequal variances by treatment group (except if convergence issue). The model will include the fixed categorical effects of treatment group (alirocumab, placebo), the dosing regimen cohort (Q2W, Q4W), the treatment-by-dosing regimen cohort interaction, the randomization strata and the continuous fixed covariate of baseline composite score value. Model assumptions for normality will be explored prior to the analysis testing. Throughout the ANCOVA model, least-square (LS) mean and standard error (SE) will be provided for each treatment group (placebo, alirocumab) regardless of the dosing regimen cohorts. LS means difference will be provided for the comparison of the alirocumab group versus the placebo group regardless of the dosing regimen cohorts, with the SE, 95% confidence intervals (CI) for descriptive purpose, using

appropriate contrasts. The corresponding effect sizes will be computed using Cohen's formulae (see Appendix G).

For the OL period, the results will be described overall in the OL population.

2.4.6 Analyses of other endpoints

All analyses/summaries for other endpoints will be performed on the safety population for the double-blind period and on the OL population for the OL period.

All measurements, scheduled or unscheduled, fasting or not fasting, will be assigned to analysis windows defined in Section 2.5.4, Table 5 and Table 6 in order to provide an assessment for Week 4 to Week 104 time points.

HsCRP and HbA_{1c}

Hs-CRP and HbA_{1c} parameters will be summarized by analysis visit using number of available data, mean, SD, median, minimum, and maximum (for hs-CRP, Q1 and Q3 will be also provided) during the treatment period. The time profile of each parameter will be also plotted with the means and the corresponding SEs for HbA_{1c} and the medians with (Q1-Q3) for hs-CRP. The incidence of PCSA at any time during the TEAE period will be also summarized using descriptive statistics.

Patients with low LDL-C

Binary endpoints defined in Section 2.1.5 will be described using count and percentage. Kaplan-Meier curves will be provided for the "Time to" variables in the double-blind treatment period. Patient without event will be censored at the end of the treatment period. For the analysis of the time to the first of the two consecutive LDL-C as defined in Section 2.1.5, patients without postbaseline LDL-C result or with only one post-baseline LDL-C result will not be included.

Creatine phosphokinase-MB and cardiac troponin

Creatine phosphokinase-MB parameter will be summarized at Week 24 on the safety population using number of available data, mean, SD, median, Q1, Q3, minimum, and maximum. In addition, similar tables as for PCSA will be provided using the normal range. This table will summarize the number (%) of patients with value >ULN during the TEAE period irrespective of the baseline level and/or according to the following baseline status categories \leq ULN, >ULN.

Cardiac troponin at Week 24 will be summarized on the safety population according to the following categories:

- <LLOQ;
- \geq LLOQ.

Urinalysis

The proportion of patients with at least one finding of proteinuria, hematuria or an abnormality on urine microscopy during the TEAE period will be summarized using descriptive statistics.

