9.3.7 CPK-MB and cardiac troponin

CPK-MB and cardiac troponin levels will be assessed at baseline and at Week 24 and in case of any clinically relevant cardiovascular effect observed in patients.

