11.4.4.5 CPK-MB and troponin

CPK-MB and troponin (value and percent change from baseline) at Week 24 will be summarized on the safety population using number of available data, mean, SD, median, Q1, Q3, minimum, and maximum for each treatment group. In addition, the incidence of PCSA at any time during the TEAE period will be summarized by treatment group using descriptive statistics.

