2.1.5 Other endpoints

Other endpoints listed below are defined using same definitions and rules as for LDL-C, when applicable (see Section 2.1.3) and include:

- The absolute change in HbA_{1c} (%) from baseline to Week 24 in the double-blind period, as well as change from baseline to Week 68 and Week 104 in the OL period. PCSA criteria for HbA_{1c} will be also used (see Appendix A).
- The proportion of patients with 2 consecutives results, spaced out by at least 21 days, of LDL-C <50 mg/dL (<1.30 mmol/L), LDL-C <25 mg/dL (<0.65 mmol/L), LDL-C <15 mg/dL(0.39 mmol/L) during each treatment period (double-blind or open-label) and the time to the first LDL-C <50 mg/dL (<25 mg/dL, <15 mg/dL respectively) for these patients within the relevant treatment period.
- Cardiac function: CPK-MB and cardiac troponin (at Visit 4 [Week 0 / Day 1] and Visit 7 [Week 24]/or early termination) and in case of any clinically relevant cardiovascular effect observed in patients.
- The percent change in hs-CRP from baseline to Week 24 in the double-blind period. Hs-CRP values greater or equal to 10 mg/L will be excluded from analyses in a second approach, since these are suggestive of concurrent infections (1). PCSA (potentially

clinically significant abnormalities) criteria for hs-CRP will be also used (see Appendix A).

• Urine test at Visit 4 (Week 0 / Day 1) and Visit 7 (Week 24)/or early termination. Macroscopy will be performed at the central laboratory. If abnormal, then a standard microscope assessment will be conducted.

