2.5.4 Windows for time points

Data analyzed by time point (including efficacy, laboratory safety data, vital signs, ADA) will be summarized using the analysis windows given in Table 5, Table 6 and Table 7. These analysis windows will be applicable for all analyses, and they are defined to provide more homogeneous data for time point-specific analyses.

Time point	Targeted study day	Analysis window in study days
	Targeted Study day	Analysis window in study days
Week 8	57	43 to 70
Week 12	85	71 to minimum (98; study day corresponding to the first
		injection with IMP from kit allocated at Week 12 re-supply
		IVRS contact)
Week 24	169	155 to 182ª

Property of the Sanofi Group - strictly confidential

19-Feb-2021		
Version	number:	2

Time point	Targeted study day	Analysis window in study days	
------------	--------------------	-------------------------------	--

Study days are calculated from the day of first double-blind IMP injection, the day of first double-blind IMP injection being Day 1. For randomized but not treated patients, Day 1 is the day of randomization.

^a 155 to 182 for patients not entering the OL period or minimum of 182 or study day corresponding to the first OL injection for patients entering the open-label extension

Time point	Targeted study day	Analysis window in study days
Week 32	57	36 to 77
Week 44	141	120 to 161
Week 56	225	204 to 245
Week 68	309	288 to 329
Week 80	393	372 to 413
Week 92	477	456 to 497
Week 104	561	540 to 581

Table 6 - Analysis windows definition for OL period

Study days are calculated from the day of first OL IMP injection, the day of first OL IMP injection being Day 1.

If multiple valid values of a variable exist within an analysis window, the value collected at the scheduled visit will be used if within the analysis window. Otherwise the nearest from the targeted study day or time will be selected. If the difference is a tie, the value after the targeted study day or time will be used

For all endpoints except PK, if multiple valid values of a variable exist within a same day, then the first value of the day will be selected when time is available, else the scheduled visit will be selected.

PK Concentration will be analyzed following time windows as defined below in Table 7. If the date of the previous injection is unknown, the alirocumab concentration will not be considered for the analysis.

PK variables	Time window (D1 = day of previous injection or day of last injection $C_{follow-up}$)	

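### SAP 2.4.6 reduces cardiac troponin to below versus at or above the LLOQ at Week 24; the abnormal-value count over the TEAE period planned in protocol 11.4.4.5 is dropped without record

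*SAP*

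**What the plan says.** **Sampling.** Protocol 9.3.7: "CPK-MB and cardiac troponin levels will be assessed at baseline and at Week 24 and in case of any clinically relevant cardiovascular effect". SAP 2.1.5 keeps the event-triggered samples in the endpoint definition: "and in case of any clinically relevant cardiovascular effect observed in patients".

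**Protocol analysis (11.4.4.5).** Two parts, for both markers. First, "CPK-MB and troponin (value and percent change from baseline) at Week 24 will be summarized on the safety population using number of available data" together with the usual location and spread statistics. Second, "the incidence of PCSA at any time during the TEAE period will be summarized by treatment group using descriptive statistics".

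**SAP analysis (2.4.6).** CPK-MB gets a continuous summary at Week 24 and a normal-range table: "This table will summarize the number (%) of patients with value >ULN during the TEAE period irrespective of the baseline level", and/or split by baseline at or below versus above the ULN. For troponin the whole plan is "Cardiac troponin at Week 24 will be summarized on the safety population according to the following categories": below the LLOQ, and at or above it.

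**Week 24 window (SAP 2.5.4).** The footnote to Table 5 sets it as "155 to 182 for patients not entering the OL period or minimum of 182 or study day corresponding to the first OL injection" for those entering the extension. If several values fall in the window, the scheduled-visit value takes precedence.

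**The concern.** Troponin is collected as a cardiac safety marker in children and adolescents. The natural question for the report is how many patients had a raised, or newly raised, value on alirocumab and on placebo at any time on treatment. The protocol's TEAE-period incidence was meant to answer it. The SAP's two-category table answers a different question: how many patients had a quantifiable value at one visit.

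The LLOQ is a property of the assay, not a limit of normality. The samples most likely to be abnormal are those drawn because of a cardiovascular effect, and a Week 24 table has no natural place for them.

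**Working it through.** The plan states no figure on this point, so the check is a comparison of the texts plus one day count.

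**1. Protocol against SAP**

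| Element in protocol 11.4.4.5 | CPK-MB in SAP 2.4.6 | Troponin in SAP 2.4.6 |
|---|---|---|
| Value at Week 24, continuous | kept | replaced by two LLOQ categories |
| Percent change from baseline | not mentioned | not mentioned |
| Abnormal values at any time in the TEAE period | count above the ULN, with optional split by baseline status | none |

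SAP Appendices A and B contain no criterion for either marker, so the protocol's PCSA analysis cannot be run as written for either. For CPK-MB the SAP substitutes the normal range; for troponin it does not. SAP Table 2 (amendment changes) and Table 3 (version 2 against version 1) mention neither the troponin change nor the dropped CPK-MB percent change.

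**2. What the LLOQ split can show**

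- LLOQ below ULN: the upper category holds both detectable values within the normal range and values above the ULN. The table cannot separate them.
- LLOQ above ULN: every value in the upper category is already elevated, and the merging problem disappears.

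The documents give neither limit, so this part is conditional.

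**3. Shift from baseline**

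A patient with quantifiable troponin at both baseline and Week 24, and a patient in whom it is quantifiable only at Week 24, fall in the same Week 24 category. Showing the baseline distribution beside it would not tell the two apart, because that is not a within-patient cross-classification. This holds wherever the LLOQ lies.

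**4. Event-triggered samples**

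- Triggered before Day 155: outside the window, not in the table.
- Triggered inside the window, with a scheduled Week 24 value also inside it: the scheduled value is used.
- Triggered inside the window, with no scheduled value there: it can stand in for Week 24.
- Triggered in the open-label period: no troponin table covers it.

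Share of the double-blind TEAE period covered by the window, under stated assumptions:

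- First open-label injection on Day 169 (assumed): Days 155 to 169 are 169 − 155 + 1 = 15 days; 15/169 = 8.9%.
- No open-label entry and last dose on Day 155 (assumed): the TEAE period ends on Day 155 + 70 = 225. The window is 182 − 155 + 1 = 28 days; 28/225 = 12.4%.

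About 88% to 91% of TEAE days therefore lie outside the window. These are days, not samples. The only scheduled post-baseline troponin is at Week 24, and it falls inside the window when the visit is on time.

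**The case against.** **A categorical summary is defensible.** SAP 2.5.1 replaces values below the LLOQ by half the LLOQ in quantitative analyses. If most troponin values are censored, means and percent changes would be largely artefact. This stands as a reason to drop the continuous summary. It does not explain dropping the count of abnormal values over the TEAE period.

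**Other outputs may show the important cases.** Protocol section 10 asks for clinically relevant abnormal laboratory values to be rechecked and documented as adverse events where applicable. Section 10.4.3 makes a laboratory finding an adverse event if, for example, it is symptomatic, needs treatment or consultation, or is serious. A raised result from a triggered sample would often qualify and reach the TEAE tables. This stands in part. A reader might infer that nothing else planned could reveal an elevation, and that is too strong. What is missing is a count of the numeric results, including silent elevations. Troponin is not among the AESIs.

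**General rules might cover it.** SAP 2.4.5.3 says normal-range tables could be provided where no PCSA criterion exists, and SAP 2.5.5 lets unscheduled values supply a time point or determine an abnormality. The first is optional, sits in another section and does not name troponin. The second has little to act on, because Week 24 is the only troponin time point and no abnormality limit is set.

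**Baseline is not ignored.** SAP 2.1.1 and 2.4.1 allow baseline safety values to be presented with the analyses. That is correct, but no shift table follows from it.

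**The change tables list only major changes.** Both sections are worded that way, so the omission may be deliberate. The departure is still recorded nowhere else in the SAP.

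**Conclusion.** The SAP departs from protocol 11.4.4.5 for troponin, gives no reason, and leaves a table that answers less than the one for CPK-MB in the same section. The missing shift from baseline and the missing TEAE-period count hold whatever the assay limits are. The merging of raised with merely detectable values holds only if the LLOQ is below the ULN.

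Three stronger readings are not supported:

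- A reader might infer that raised troponin can never be identified. Without the LLOQ and ULN that is an assumption, and it would concern the planned table, not the underlying data.
- A reader might infer that all event-triggered samples are excluded. One can stand in for the Week 24 value.
- A reader might infer that CPK-MB follows the protocol in full. Its percent change is also dropped.

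The number of patients affected cannot be derived; there may be no triggered samples at all. Troponin is a descriptive endpoint and no efficacy or inferential conclusion depends on it. The point is minor but worth correcting, because the data are already collected.

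**What to change.** In SAP 2.4.6:

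1. Add for troponin the table already written for CPK-MB: number and percentage of patients with a value above the ULN at any time in the TEAE period, counting scheduled, unscheduled and event-triggered samples, overall and by baseline status (at or below the ULN, above the ULN), by treatment group.
2. Keep the LLOQ categories at Week 24 as supplementary rows, and state the assay's LLOQ and ULN in a footnote so that a reader can see whether the two cuts differ.
3. Record as departures from protocol 11.4.4.5, with the reason (for example, censoring at the LLOQ), the dropped value and percent-change summary for troponin and the dropped percent change for CPK-MB.

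The cost is one extra set of rows in an existing table and a few lines of SAP text. It needs no new data, no further testing and no protocol amendment.
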